7.2 Recording Serious Adverse Events and Serious Adverse Reactions

The definition of a serious adverse event (SAE) will be any medical event that:

- Results in death.
- Is life-threatening [refers to an event during which the participant was at risk of death at the time of the event; it does not refer to an event which might have caused death had it been more severe in nature].
- Requires hospitalisation, or prolongation of existing hospitalisation.
- Results in persistent/significant disability or incapacity.
- Is a congenital abnormality or birth defect.
- Other important medical events that, based upon appropriate medical judgment, may jeopardise the participant and may require medical or surgical intervention.

All SAEs and Serious Adverse Reactions (SARs) will be recorded in the 'Investigator Site File and the NWORTH trial unit manager will be informed immediately. The principal investigator or chief investigator at the treatment site will scan and email details of the SAE or SAR to the NWORTH trial unit manager via the NWORTH Sciatic trial manager who will record the information on the trial master file. Following the initial report, all SAEs should be followed up to resolution wherever possible and further information may be requested by NWORTH. The participant will be identified only by the participant's identification number. The participant's name should not be used on any correspondence. Once an SAE is received at NWORTH, it will be evaluated by the CI (or his delegate) for seriousness, expectedness and causality. The causality and expectedness assessment given by the PI cannot be overruled by the CI (or his delegate) and in the case of disagreement; both opinions will be provided with the report.

All SAEs will be reported to the sponsor's representative in Bangor University within 24 hours of being discovered, oversight and pathways for adverse incident reporting during the trial period will be managed by the sponsor's representative within the Healthcare and Medical Sciences Academic Ethics Committee (HCMS AEC) reporting to a standing –committee for trials within the University Ethics Committee (UREC) on behalf of Council. On an annual basis a 'Development Safety Update Report' (DSUR) containing a list of all SAEs and SARs will be submitted to the

MHRA. In addition, all Suspected Unexpected Serious Adverse Reactions (SUSARs) will be reported to the MHRA within seven days (fatal/life threatening) or fifteen days (non-fatal/non-life threatening). They will also be reported to the chair of the DMEC and the research ethics committee. NWORTH will report a list of all SAEs (expected and unexpected) and any other safety recommendations to all PIs every six months, and to the REC every 12 months, throughout the course of the trial. The frequency of PI safety reports may be reviewed and amended as necessary

Training on the adverse events and serious adverse events reporting procedure will be given to all relevant trial staff.

8. Statistics

8.1 Sample Size

From the Weighted Mean Difference (WMD) in our previous meta-analysis we found a relative improvement of eight points in the ODI at six months follow-up in the group receiving biological agents compared with placebo with a standard deviation of 16, giving an effect size of 0.5. In order to detect a more conservative effect size of 0.4 with 90% power, with a significance level of 5% for a two-tailed t test, a sample size of 133 in each treatment group will be needed. We will aim for a 90% return rate of the final questionnaires, but for a more conservative retention rate of 80% 332 will need to be recruited. If, as is likely, there is any correlation between the baseline and outcome measure, the size of effect detectable will be smaller (or the power to detect a 0.4 effect enhanced).

8.2 Recruitment rate

Calculations of recruitment rates for the SCIATiC trial were based on data available from an observational study, led by co-applicants at Keele, which recruited adult patients seeking treatment in primary care for low back-related leg pain including sciatica (ATLAS cohort), the ATLAS study recruited 609 patients from 17 general medical practices (approximate total adult population 90,200) over 24 months. Analysis of the recruitment data shows that 219 (36%) of this cohort had sciatica with pain in one leg only (with >80% diagnostic confidence) with a Roland Morris Disability Questionnaire score >7 (equivalent to ODI≥30). On average per month, 86 potential participants were identified by GP's and referred to the ATLAS study 54 attended the physiotherapy-led research clinic, 25 gave consent and were eligible for the study, nine of whom had a clinical diagnosis of sciatica (spinal nerve root pain) satisfying the condition described above in term of disability score and diagnostic confidence. Based on these figures and taking into account that in the ATLAS cohort, approximately nine participants per month were recruited, and making the

assumption that half this number would consent to be randomised in a RCT, our target rate of recruitment will be four participants per collaborating centre per month with centres covering similar sized populations. For the SCIATiC trial, the collaborating centres will recruit from GP practices with a combined registered population of at least.

8.3.1 Primary analysis

The main outcome variable will be the ODI measured at 12 months. A linear mixed model approach for repeated measures will be used to assess the effects of Time, Group and time*Group will further describe and explain the overall finding (the interaction term will assess whether the effect of the intervention is the same or not at each time point). This model will be fully defined in the SAP prior to all analyses.

8.3.2 Secondary analysis

Secondary continuous outcome variables will be assessed in a similar way to the primary outcome variable, with the exception of time to referral for surgery which will be measured from trial entry (this is the date of second consent) and analysed using Kaplan-Meier survival analyses and the log rank test. Dichotomous variables will be explored using logistic regression. These analyses will be repeated using prespecified participant subgroups (including the presence of neurological deficit on entry to the trial and MRI findings). Subgroups will be defined within the SAP prior to analyses beginning.

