4.5 Magnetic Resonance Imaging

Participants who have given initial informed consent will receive magnetic resonance imaging (MRI) to exclude serious spinal pathology, but the presence or absence of a disc prolapse will not be used as an inclusion criterion. The MRI scans will be read and reported by a local radiologist using a trial SOP at each treatment site, who is independent of the trial team and only results which show serious pathology or suspected serious pathology will be revealed to the research team, referring GP and the musculoskeletal clinician who will exclude the participant and refer for urgent assessment. Otherwise the research team will be informed that no serious spinal pathology was identified. The findings of the MRI will only be available to the participants treating clinician after completion of the study. Individual results will be made available if a report is needed in an emergency, or if a spinal surgery or epidural injection referral is being contemplated and will be shared with the clinical team, referring GP and the musculoskeletal clinician The MRI findings will also be used in a planned a priori sub-group analysis. For clinical purposes each site will provide a clinical report of the MRI from radiologists in each site. For the purpose of reporting standardised findings for research radiologists from Betsi Cadwaladr

University Health Board (BCUHB) [name] and Keele University will report all of the MRI for all trial participants. The radiologist will interpret the report according to the MRI findings only.

Centres	T-SPOT	Chest X-Ray	IGRA
London		Х	Х
Keele	Х	Х	
Nottingham	Х	Х	
Cardiff	Х	Х	
North Wales	Х	Х	

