4.9 Randomisation

After completion of the second consent form and baseline outcome measures have been collected, participants will be individually randomised. Randomisation to SCIATiC trial will be achieved by secure web access to the remote randomisation system at NWORTH at Bangor University. This system will be maintained and monitored independently of the trial statistician and any trial staff who need to remain blind to the treatment allocation. In order to protect against subversion while ensuring that the trial maintains good balance to the allocation ratio of 1.1, both within each stratification variable and across the trial, the randomisation will be performed using a dynamic adaptive randomisation algorithm [36] Participants will be stratified by: (1) treatment centre and (2) presence of neurological signs (motor weakness or sensory loss). The research physiotherapist who obtained informed consent will request the randomisation code from the web-based randomisation system the result of which will be e-mailed to the pharmacy and the rheumatology nurse, but not the research physiotherapist. The dispensing pharmacist will log and dispense the appropriate injection in line with MHRA guidelines. The injection should be given on the day of randomisation, however, if this is not possible a further appointment will be arranged by the research physiotherapist so that the treatment can be given within three days from randomisation.

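### The protocol's only stated subgroup method, repeating the analyses by subgroup, does not test whether the treatment effect differs between subgroups

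*Protocol*

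**What the plan says.** Protocol Section 8.3.2 (Secondary analysis) covers secondary continuous outcomes, time to referral for surgery and dichotomous outcomes, and then states: "These analyses will be repeated using prespecified participant subgroups". It names neurological deficit at entry and MRI findings among these subgroups. The sentence after it sends the choice of subgroups to the SAP: "Subgroups will be defined within the SAP prior to analyses beginning".

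Both named subgroups are prominent elsewhere. Section 4.5 says "The MRI findings will also be used in a planned a priori sub-group analysis". Neurological signs are a randomisation factor in Section 4.9: "Participants will be stratified by: (1) treatment centre and (2) presence of neurological signs (motor weakness or sensory loss".

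The only interaction in the clinical analysis is time by group, in Section 8.3.1, where "the interaction term will assess whether the effect of the intervention is the same or not at each time point". That concerns time points, not patient subgroups. Section 8.3.3 also mentions interaction effects, but for multivariate sensitivity analyses in the economic evaluation.

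**The concern.** The question behind a subgroup analysis is whether the effect of adalimumab differs between, say, patients with and without neurological deficit. Running the same model separately in each subgroup answers another question: is the effect distinguishable from zero here? Each subgroup is smaller than the trial. One can therefore reach significance and the other miss it when the true effect is identical in both.

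The consequences could be practical. Disc prolapse on MRI is deliberately not an inclusion criterion (Sections 4.1.5 and 4.5), and MRI findings are kept for a subgroup analysis instead. An apparent contrast between MRI groups could influence who is offered a drug that Section 1 calls expensive. Section 8.3.3 also plans stratified cost-effectiveness analyses in pre-specified subgroups, so a chance contrast could carry over into the economic conclusions. Because the sentence follows all the secondary outcomes, repeating everything by subgroup also multiplies the comparisons.

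**Working it through.** **Inputs.** From Section 8.1: "In order to detect a more conservative effect size of 0.4 with 90% power", "with a significance level of 5% for a two-tailed t test", 133 per arm, 80% retention, 332 recruited. Allocation is 1:1 (Section 4.9). The protocol gives no subgroup prevalence, so the splits are assumptions: 50:50 (66 per arm in each stratum, rounded down) and 70:30 (93 and 40 per arm).

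**The plan's own figure.** A two-sided 5% t-test at effect size 0.4 with 133 per arm has power 0.901, and 133 is the smallest n reaching 90%. Then 266/0.8 = 332.5, against 332 stated. The sample size reproduces.

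**Discordance under one common effect.** If the two strata have power p1 and p2, the chance that exactly one is significant is

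P = p1(1 − p2) + p2(1 − p1).

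t-test power comes from the noncentral t distribution with noncentrality d√(n/2).

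| True effect in both strata | Split | p1, p2 | P |
|---|---|---|---|
| 0.4 SD | 50:50 | 0.626, 0.626 | 2 × 0.626 × 0.374 = 0.468 |
| 0.4 SD | 70:30 | 0.774, 0.424 | 0.774 × 0.576 + 0.424 × 0.226 = 0.542 |
| 0.2 SD | 50:50 | 0.207, 0.207 | 2 × 0.207 × 0.793 = 0.33 |
| 0.2 SD | 70:30 | 0.274, 0.143 | 0.274 × 0.857 + 0.143 × 0.726 = 0.34 |
| 0 | any | 0.05, 0.05 | 2 × 0.05 × 0.95 = 0.095 |

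**With baseline adjustment.** Section 8.1 expects some baseline correlation. With an assumed correlation r, the effective effect is 0.4/√(1 − r²): 0.462 at r = 0.5 and 0.500 at r = 0.6.

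- r = 0.5, 50:50: 2 × 0.750 × 0.250 = 0.375
- r = 0.5, 70:30: 0.880 × 0.468 + 0.532 × 0.120 = 0.476
- r = 0.6, 50:50: 2 × 0.814 × 0.186 = 0.303
- r = 0.6, 70:30: 0.924 × 0.402 + 0.598 × 0.076 = 0.417

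The range is therefore about 30-48%.

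**Interaction test.** When the effects are equal, a two-sided 5% test of the difference between strata is falsely positive 5% of the time, whatever the overall effect. One million simulated trials at 0.4 SD gave 0.050 for each split.

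Its power is limited. With 266 analysed, the standard error of the difference in SD units is √[4/(266f) + 4/(266(1 − f))], where f is the share in the first stratum. That is 0.245 at f = 0.5 and 0.268 at f = 0.7. For a true interaction of 0.4 SD, the ratios 0.4/0.245 = 1.63 and 0.4/0.268 = 1.49 give power of 37% and 32%, before any gain from baseline adjustment.

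**The case against.** The strongest reply is that the protocol does not contain the error. A reader might infer that it has chosen separate significance tests in place of an interaction test. The text does not support that. It does not rule out an interaction term, and it nowhere says that p-values from the subgroups will be compared or a difference inferred from them. Repeating models by subgroup to obtain estimates is compatible with an added interaction test. This part of the reply stands.

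A second reply is that model specification belongs to the SAP: Section 8.3 promises a full one, and Section 8.3.1 leaves the primary model to it. The SAP is not shown and may supply the test. But Section 8.3.2 does more than defer. It states a method and passes on, by name, only the definition of the subgroups. A SAP that followed it literally would have no test of effect difference.

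Third, the figures use the ODI design assumptions, while the sentence sits under secondary outcomes, for which no effect size is given. That is correct: 47-54% cannot be attached to those outcomes. They also need an assumed split and a true effect of 0.4 SD in everyone.

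Fourth, discordance is a false claim only if someone reads it as a difference, so setting it against a 5% type I error is conditional on that reading. This also stands.

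**Conclusion.** The point holds as an incomplete method. The one subgroup procedure that the protocol states cannot answer the subgroup question, and no treatment-by-subgroup interaction test is named anywhere. Whether the primary ODI is included is unclear.

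The size is conditional on reading the results by significance in each subgroup. With 133 per arm, an assumed 50:50 to 70:30 split and equal true ODI effects, a misleading contrast would appear in about 47-54% of trials at 0.4 SD, about 30-48% with an assumed baseline correlation of 0.5-0.6, about 33% at 0.2 SD unadjusted, and 9.5% with no effect. An interaction test gives 5%.

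It would go too far to conclude that the trial will report a false subgroup finding about half the time, or that it will claim benefit only with prolapse. The MRI subgroups are not yet defined, and no rule for interpreting the subgroup results is stated.

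**What to change.** Replace the subgroup sentence in Section 8.3.2 with wording such as:

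> Differences in treatment effect between pre-specified subgroups will be assessed by a treatment-by-subgroup interaction term in the same model as the main analysis, first for the ODI at 12 months, and reported as an estimate with 95% confidence interval. Estimates within subgroups, with confidence intervals, are descriptive only. Any subgroup analysis of secondary outcomes will use the same approach and be labelled exploratory.

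This also settles whether the primary outcome is covered. The subgroup definitions can stay with the SAP.

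The cost is one changed sentence, with no effect on sample size, data collection or conduct. The drawback is low power: about 32-37% for an interaction as large as the design effect of 0.4 SD. The report should say this, so that a non-significant interaction is not taken as evidence of equal effects.

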8.3.3 Economic analysis

The health economic analysis will adopt the perspective of the National Health Service (NHS) and Personal Social Services (PSS) and additionally indirect costs e.g. time off work (secondary analysis). Costs will include those of treatment, tests, procedures and investigations, contact with primary and secondary care services and personal social services. Resource use will be obtained from participants' selfreporting of resource use, captured by questionnaire administration [48, 49]. Unit cost data will be obtained from standard sources such as Curtis [56]. NHS reference costs [57] and other resources such as the BNF [31]. The primary economic outcomes will be the incremental cost per QALY gained, estimated by administering the EQ-5D-5L at each follow-up point. The number of QALYs experienced by each participant will be calculated as the area under the curve, using the trapezoidal rule, applying the UK tariffs and corrected for baseline utility score. Where appropriate, missing resource use or health outcome data will be imputed [57]. Non-parametric bootstrapped 95% confidence intervals will be estimated (10,000 replicates). We will also employ simple parametric approaches for analysing cost and QALY data that assume normal distributions given the large samples where the near-normality of sample means is approximated. Should the data indicate otherwise, we will develop a generalised linear model, to deal with problems such as skewness. Stratified cost-effectiveness analyses will be conducted on important, pre-specified participant subgroups. Total costs will be combined with QALYs to calculate the incremental cost-utility ratio of the package of adalimumab plus physiotherapy compared with 0.9% Sodium Chloride injection plus physiotherapy. Estimates of ICURs will be compared with the £20,000 to £30,000 per QALY threshold of cost-effectiveness, and a range of one-way sensitivity analyses will be conducted to assess the robustness of the analysis. Multivariate sensitivity analyses will be applied where interaction effects are suspected. The joint uncertainty in costs and benefits will be considered through the application of bootstrapping and the estimation of cost-effectiveness acceptability curves [58].

9. Trial Management

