2.1 Trial Objectives

1. To evaluate the effectiveness of subcutaneous injections of adalimumab plus physiotherapy compared with placebo injection of 0.9% sodium chloride plus physiotherapy for patients with sciatica who have failed first line primary care treatment. Potential participants will be identified during primary care consultation, after referral to musculoskeletal service or following a practice database search. The primary effectiveness outcome will be sciatica related health status using the Oswestry Disability Index [32]. Secondary effectiveness outcomes will include pain intensity, location, duration and anticipated trajectory; the risk of poor outcome; psychological measures including fear avoidance beliefs, self-efficacy, anxiety and depression; employment status; adverse effects.

2. To evaluate the cost-effectiveness of subcutaneous injections of adalimumab plus physiotherapy compared with placebo injection of 0.9% sodium chloride plus physiotherapy for patients with sciatica who have failed first line primary care treatment from a health service and personal social care perspective. The primary economic outcome will be the incremental cost per Quality Adjusted Life Year (QALY) gained. QALYs will be estimated by administering the EQ-5D-5L [33] at each follow-up visit.

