6.1.4 Use of health care and social care services

• Resource Use Questionnaire (RUQ) [48, 49].

This is used for collecting retrospective information about trial participants' use of health and social care services, out of pocket expenses and lost earnings. It will be administered at baseline, six weeks, six and twelve months follow-up.

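### Section 8.3.3 names a baseline adjustment for QALYs but none for costs, although baseline resource use is collected, so the incremental cost may be less precise than the data allow

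*Protocol*

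**What the plan says.** The ratio of incremental cost to QALYs gained is the headline economic result. Protocol section 2.1: "The primary economic outcome will be the incremental cost per Quality Adjusted Life Year (QALY) gained".

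Section 8.3.3 treats its two halves differently.

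- **QALYs:** a trapezoidal area under the EQ-5D-5L curve, "applying the UK tariffs and corrected for baseline utility score".
- **Costs:** perspective, sources of resource use and unit costs, imputation and bootstrapped intervals are all given. On modelling it adds "We will also employ simple parametric approaches for analysing cost and QALY data that assume normal distributions", and then "Should the data indicate otherwise, we will develop a generalised linear model, to deal with problems such as skewness". No covariate is named.
- **The ratio:** "Total costs will be combined with QALYs to calculate the incremental cost-utility ratio".

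On the RUQ, section 6.1.4 says "It will be administered at baseline, six weeks, six and twelve months follow-up", and the data collection schedule also marks it at the randomisation visit. No section says what the baseline record is for.

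Section 4.9 stratifies randomisation by treatment centre and by neurological signs, not by earlier use of services.

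**The concern.** A pre-randomisation measure of resource use will exist for most participants, and nothing is planned for it. If earlier use predicts later use, part of the spread in follow-up cost can be explained by a variable already on file. Leaving that variable out gives a wider interval for the incremental cost than necessary, and so a wider bootstrap scatter and a flatter acceptability curve.

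It also means that if heavier users of services happen to fall in one arm, the estimated cost difference carries that imbalance in full. The design does not guard against this, because prior use is not a stratification factor.

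The wording matters more in 8.3.3 than it would elsewhere. Sections 8.3.1 and 8.3.2 expressly pass their model and subgroup definitions to the SAP. Section 8.3.3 describes the economic analysis in some detail and contains no such deferral for the cost model.

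**Working it through.** **The plan's own figure.** The protocol gives no standard deviation, precision or power for costs. Its only sample-size figure concerns the ODI (section 8.1): "detect a more conservative effect size of 0.4 with 90% power, with a significance level of 5% for a two-tailed t test", for which "a sample size of 133 in each treatment group will be needed". The two-sample t test gives 132.3, hence 133 per arm, with power 0.901 at 133. Inflating for 80% retention, 266 / 0.8 = 332.5, against the stated 332, a rounding difference. The figure reproduces. It is used below only as the number analysed: 133 per arm, 266 in all.

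**Inputs**

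- n = 133 per arm (section 8.1).
- r, the within-arm correlation between baseline and follow-up cost: not in the protocol. Assumed range 0.1 to 0.6.

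**Step 1: precision.** With linear adjustment for baseline cost:

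- SE(adjusted) = SE(unadjusted) × √(1 − r²)
- narrowing of the interval = 1 − √(1 − r²)
- equivalent number analysed = 266 / (1 − r²)

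| r | 1 − r² | √(1 − r²) | Interval narrower by | Equivalent to analysing |
|---|---|---|---|---|
| 0.1 | 0.99 | 0.995 | 0.5% | 269 |
| 0.2 | 0.96 | 0.980 | 2.0% | 277 |
| 0.3 | 0.91 | 0.954 | 4.6% | 292 |
| 0.4 | 0.84 | 0.917 | 8.3% | 317 |
| 0.5 | 0.75 | 0.866 | 13.4% | 355 |
| 0.6 | 0.64 | 0.800 | 20.0% | 416 |

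**Step 2: does the formula hold for skewed costs, and is there bias?** Lognormal baseline and follow-up costs were simulated with no true difference, 133 per arm, 4,000 replicates per r. The ratio of adjusted to unadjusted standard error was 0.98, 0.90 and 0.80 at r = 0.2, 0.4 and 0.6, against 0.98, 0.92 and 0.80 from the formula. The average estimated difference, adjusted or not, lay between −0.008 and 0.003, on a scale where the cost SD is √(e(e − 1)) ≈ 2.2. Both estimators are centred on the truth.

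**Step 3: chance imbalance.** In SD units, the standard error of the difference in mean baseline cost is √(2/133) = 0.123, so its 95% range reaches 1.96 × 0.123 = 0.24 SD. An imbalance of that size would move the unadjusted cost difference by r × 0.24 follow-up SDs: 0.02 SD at r = 0.1, 0.07 SD at r = 0.3 and 0.12 SD at r = 0.5. As a share of that difference's own standard error this is r × 1.96, or 0.20, 0.59 and 0.98. Adjustment removes it.

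**Step 4: can adjustment hurt?** One extra covariate inflates the variance by about 1/(266 − 4) = 0.4% (normal-theory approximation). That is recovered once r² exceeds about 0.004, so r above about 0.06.

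**The case against.** **Silence is not a decision.** A reader might infer that the protocol has chosen to analyse costs without adjustment. It has not said so. Forming the ratio from total costs describes how the ratio is built, not which covariates enter the cost model, and either the parametric methods or the generalised linear model could carry baseline cost. The analysis plan, which is not shown, may already name it. This stands, and limits the point to what 8.3.3 names and omits.

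**The asymmetry has a reason.** Baseline utility is the first point of the area under the curve, so a baseline difference enters the QALY difference mechanically. Baseline resource use precedes randomisation and forms no part of follow-up cost. Correcting QALYs alone is therefore coherent, and a reader who infers an internal contradiction goes too far. This also stands, but it does not remove the gain from using baseline cost.

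**No bias.** A reader might infer that the incremental cost is biased. Randomisation rules that out in expectation, and a valid unadjusted interval already allows for chance imbalance.

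**The correlation may be low.** Participants have had symptoms for less than six months, with no earlier sciatica episode in that time and no previous lumbar surgery (sections 4.2 and 4.3). Varying numbers of physiotherapy sessions and possible later surgery arise after randomisation. These could hold r down. The trial drug cost bears less on this, since it is nearly constant within the active arm. This stands as uncertainty about size.

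**Skewness.** Section 8.3.3 provides for skewed data without predicting them. The point does not depend on skewness.

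**Conclusion.** The point holds as a minor improvement. Section 8.3.3 fixes a baseline correction for QALYs, names none for costs, and leaves the baseline RUQ without a stated use. An analyst who followed it literally would obtain an unbiased incremental cost with some avoidable imprecision, exposed to chance imbalance in prior use.

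The size is conditional on an assumed r: small up to about 0.3 (interval narrower by at most about 5%), worthwhile at 0.5 (about 13%). The figures also assume 133 analysed per arm and a roughly linear relation between baseline and follow-up cost. The documents do not support calling this an error in the plan or a threat to the validity of the economic conclusion.

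**What to change.** State in section 8.3.3 that incremental costs will be estimated by regression adjusted for baseline RUQ cost, alongside QALYs adjusted for baseline utility, and that the two adjusted estimates will be bootstrapped together, resampling participants, so that their correlation is kept. A bivariate regression of costs and QALYs is one acceptable way; separate regressions within each bootstrap sample are another. If the generalised linear model is used with a non-identity link, report the adjusted difference in mean cost in pounds, since that is what enters the ratio.

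Settling this before data release also avoids a later choice between adjusted and unadjusted costs.

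The cost is a sentence in the protocol and matching text in the analysis plan, plus the work of costing the baseline RUQ items and a stated rule for missing baseline values. No new data collection is needed.
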